13.5 Baseline Screening Procedures

Baseline-screening samples will be taken on the day following the-14 day pre-test period. Subjects will not shower at least 72 hours prior to being sampled. Subjects will don a disposable undergarment prior to baseline screening procedures and will be examined physically to ensure that there is no evidence of injury, dermatosis, folliculitis, or dermatitis present at the sampling sites (Section 14.2). A subject will be dismissed from the study if skin irritation score of 1 is observed on the test sites. If the subject continues to meet the qualification criteria, they will be sampled using the Cylinder Sampling (Scrub Cup) Technique (Section 13.7) at the center of the sampling areas on the skin of the inguina and abdomen (Appendix 2). There will be a minimum of 72 hours between the time the screening period ends and the experimental period begins. Based upon adequate screening microbial counts, subjects will be eligible to continue into the treatment phase of the study. Subjects may qualify on one or two anatomical site(s) and be admitted into testing for those anatomical site(s) only, although if more subjects qualify for treatment than can be treated in a given time period, preferential admittance into the treatment phase will be given to subjects qualifying in both the abdominal and inguinal test areas.

Baseline criteria for qualification for the test period are $\geq 3.11 \log_{10} \text{ CFU/cm}^2$ from the skin of the abdomen, and/or $\geq 5.50 \log_{10} \text{ CFU/cm}^2$ from the skin of the groin.

There will be a minimum of 72 hours between baseline screening procedures and treatment day procedures. Based upon achieving adequate baseline screening microbial counts, subjects will be eligible to continue to treatment day procedures.

13.6 Treatment Day Procedures

Prior to sampling, the subjects will be questioned regarding adherence to the qualification criteria.

Subjects will don a disposable undergarment and be examined physically to ensure no evidence of injury, dermatosis, or dermatitis is present in the test areas. One sterile surgical marker will be used per subject. The marker will be used to demarcate a 5" × 5" areas of skin on the right and left sides of the abdomen, adjacent to the navel that appear to be similar in condition. The marker will again be used to demarcate 2" x 5" areas of skin in the inguinal areas that appear to be similar in condition. During treatment day procedures, subjects will wear disposable gloves to guard against contamination of the test sites.

Subjects will be sampled for treatment day baseline microbial populations on randomly assigned sites of the abdominal and inguinal areas on both sides (Appendix 2). The Cylinder Sampling (Cup Scrub) Technique (Section 13.7) will be used for baseline and post-treatment samples.

All product treatments for a subject will be completed on a single day (Treatment Day). The test materials will be applied to the test sites in accordance with the randomization schedule using repeated back-and-forth strokes for 3 minutes on both abdominal and inguinal test sites with a dry time of 1 minute. Detailed instructions on product application are presented in Appendix 1. All test materials will be weighed before and after application and the weights will be recorded. All subjects will have samples collected 10 minutes \pm 30 seconds and 6 hours \pm 30 minutes post product application on both abdomen and inguinal sites. All sampling times will be calculated from the completion of the dry time of each product following application.

Following collection of the last 6 hours \pm 30 minutes post-product application sample of a test site, the remaining test material will be wiped/cleansed from the test site with a mild soap and/or tap water; test sites will be dried with paper towel.

Cylinder Sampling (Scrub Cup) Technique 13.7

Abdomen and Inguinal Samples

A sterile cylinder with inner diameter of 3.46 cm² will be held firmly onto the test site to be sampled. A 3 mL aliquot of sterile Sampling Solution (SS) will be instilled into the cylinder, and the skin inside the cylinder will be massaged in a sweeping manner for 1 minute with a sterile rubber policeman. The SS will be removed with a sterile pipette and transferred to a sterile test tube. These procedures will be repeated for a second time. The second recovered aliquot will then be pooled in the test tube with the first aliquot, and the samples plated in duplicate using the appropriate media.

Diluting, Plating, and Counting 13.8

Aliquots of the microorganism suspension (100 dilution) will be serially diluted in sterile Butterfield's Phosphate Buffered Water (PBW), as appropriate. Serial dilution and plating will be completed within 30 minutes. Duplicate pour plates will be prepared from appropriate dilutions with Tryptic Soy Agar with product neutralizers (TSA+) and incubated at 30 °C \pm 2 °C for 72 hours \pm 4 hours. Following incubation, plates may be refrigerated for approximately 48 hours prior to counting.

Colonies will be manually counted and data recorded on appropriate data collection forms for each subject.

Blinding 13.9

The Investigational Product and Vehicle Control will be blinded. The Active Control (SAGE) cannot be blinded, due to package labeling of the marketed product. In order to guard against any bias of the study outcome, technicians who participate in product application or sample collection from subjects during treatment day procedures will not participate in the processing of samples. The technicians processing samples and/or counting the resultant plates will be blinded to the study randomization during the data

This Protocol has been approved by the GIRB on 09 [20]

gathering processes. In the event that data and calculations are handled by BSLI staff, the plate counts and calculations will be reviewed and/or approved by separate individuals prior to being entered into a data spreadsheet where product information (unblinding) would occur.

The Sponsor Quality Assurance Manager will provide the code translation to BSLI Director of Quality Assurance in individual sealed envelopes (one for each treatment code), which will be secured by BSLI Director of Quality Assurance and will remain unopened in the study file. If an emergency requires unblinding, the envelope corresponding to the treatment code that is associated with the Adverse Event will be opened by BSLI Director of Quality Assurance, or designee to reveal the treatment identification for that single treatment. If possible, the Principal Investigator or designee will contact the Sponsor with notification of the intent to unblind the treatment codes prior to actual unblinding. If it is not possible to notify the Sponsor prior to the unblinding, the Principal Investigator or designee will contact the Sponsor immediately following the unblinding procedure and follow with a written notification to document the exact manner in which the code was unblinded and the justification for the unblinding. The Principal Investigator or designee shall also provide written notification of the unblinding to the IRB. BSLI Director of Quality Assurance will communicate the treatment identification of the code associated with the AE to only the study personnel who require the information to manage the emergency.

13.10 Data Handling

The estimated log₁₀ number of viable microorganisms per cm² recovered from each sample site will be designated the "R-value."

To convert the volumetric measure of the sample into the number of colony-forming units per square centimeter (cm²), the following formula will be employed:

$$R = \log_{10} \left[\frac{F\left(\frac{\sum c_i}{n}\right) 10^{-D}}{A} \right]$$

where:

R = the average colony-forming unit count in log_{10} scale per cm² of sampling surface

F = total number of mL of stripping fluid added to the sampling cylinder; in thisstudy, F = 6 mL for all samples

 $\frac{\sum c_i}{n}$ = average of the duplicate colony counts used for each sample collected

D =dilution factor of the plate counts

A = inside area of the cylinder in cm²; in this study, $A = 3.46 \text{ cm}^2$ (2.1 cm i.d.)

NOTE: The reason that a log₁₀ transformation will be performed on the collected data is to obtain a linear scale. A linear scale, more appropriately a log₁₀ linear scale, is a basic requirement of the statistical models used in this study.

If colonies on one of the plates are uncountable, the count from the remaining plate will be used. In order to avoid potential calculation problems due to taking the logarithm of zero, counts of zero will be considered 1 for further calculations.

Data collected from subjects with low test-day baseline counts on an anatomical test site ($< 3.11 \log_{10} \text{CFU/cm}^2$ from the skin of the abdomen, or $< 5.50 \log_{10} \text{CFU/cm}^2$ on the skin on the inguen) will not be used in the mITT Efficacy Analyses (Section 15.0).

14.0 ASSESSMENT OF SAFETY

14.1 **Safety Assessments**

The subject's safety will be monitored by evaluations of reactions observed on the skin of the test sites and any adverse reactions. Adverse reactions will be documented per BSLI Standard Operating Procedure, reported as an Adverse Event, and followed to resolution.

14.2 **Evaluation of Test Sites**

Prior to product application and before any subsequent samples, test site erythema, edema, rash, and dryness will be rated on a 4-step scale, the Skin Irritation Scoring System (Draize). If a subject receives a score of 1 for erythema, edema, rash, and/or dryness prior to Screening Baseline Day or product application on Treatment Day, they will be dismissed from testing. If a subject receives a score of 3 for erythema, edema, rash, and/or dryness at any point in the study, they will be dismissed from testing and reported as an adverse event. (Note: Skin irritation scores of 1 or 2 are expected after sampling and product application procedures and are not grounds for dismissal and will not be considered adverse events.)

SKIN IRRITATION SCORING SYSTEM (Draize)

	0	No reaction
E 41	1	Mild and/or transient redness limited to sensitive area
Erythema	2	Moderate redness persisting over much of the product-exposed area
	3 *	Severe redness extending over most or all of the product-exposed area
	0	No reaction
17.1	1	Mild and/or transient swelling limited to sensitive area
Edema	2	Moderate swelling persisting over much of the product-exposed area
	3 *	Severe swelling extending over most or all of the product-exposed
0		No reaction
Rash	1	Mild and/or transient rash limited to sensitive area
Rasn	2	Moderate rash persisting over much of the product-exposed area
	3 *	Severe rash extending over most or all of the product-exposed area
0 No reaction 1 Mild and/or tr		No reaction
		Mild and/or transient dryness limited to sensitive area
Dryness	2	Moderate dryness persisting over much of the product-exposed area
	3 *	Severe dryness extending over most of all of the product-exposed area

^{*} A score of 3 in one or more of the conditions evaluated represents significant irritation and qualifies as an Adverse Event.

14.3 Adverse Events

Adverse Events will be documented for all subjects from the time of the clipping appointment to the time of discharge from the study. Adverse Events will be categorized in relationship to the product that was applied to the specific skin site. In case of a medical emergency, 911 will be called from the laboratory facility and general first aid administered until Emergency Medical Service arrives. Medical facilities/personnel are in close proximity.

In the event that either the Principal Investigator or the Sponsor determines that continuation of the study poses a hazardous risk of serious injury or death to the subjects, the study will be stopped.

14.3.1 Definitions

14.3.1.1 Adverse Event/Experience

An Adverse Event/Experience is any unexpected or undesirable experience occurring to a subject during a study, which may or may not be related to a test material. All adverse event/experiences will be recorded and reported using Adverse Event Form (Appendix 3) according to the Standard Operating Procedures of the Testing Facility.

All Adverse Events, regardless of severity or the cause/effect relationship, are to be recorded. The severity of the effect will be noted as "Mild," "Moderate," or "Severe" according the following definitions:

Mild Awareness of sign(s) or symptom(s), but easily tolerated.

Moderate Discomfort to a degree as to cause interference with normal daily

life activities and /or requiring medication.

Severe Incapacity with inability to work or do usual daily life activities

and requiring medical attention/intervention.

14.3.1.2 Causal Relations of Adverse Event/Experience

When determining the causal/effect relationship to a test material, the relationship will be described as "None," "Possible," "Probable," or "Definite." The following definitions will be utilized:

None No association to a test material. Related to other etiologies such

as concomitant medications or conditions or subject's known

clinical state.

Possible Uncertain association. Other etiologies are also possible.

Probable Clear-cut association with improvement upon withdrawal of a test

material. Not reasonably explained by the subject's known clinical

state.

Definite An adverse event with a clear-cut temporal association with

exposure to study materials and cannot reasonably be explained by the subject's known clinical state. Association with study material

is confirmed by laboratory if possible.

14.3.1.3 Serious Adverse Event/Experience – During this Study

A Serious Adverse Event/Experience is any adverse experience occurring that results in any of the following outcomes:

Death:

A life-threatening adverse drug experience;

Inpatient hospitalization or prolongation of existing hospitalization;

A persistent or significant disability/incapacity;

Congenital anomaly/birth defect;

An important medical event that may require medical or surgical intervention to prevent one of the previously listed outcomes.

14.3.1.4 Unexpected Adverse Event/Experience

An Unexpected Adverse Event/Experience is any adverse drug event/experience not listed in the current labeling for a test material or the current investigator's brochure. Where test product labeling or investigator's brochure is not available, anticipated experiences will be based on the known pharmacological/toxicological properties of a test material or ingredients.

14.3.2 Follow-up

If an adverse event/experience related to the study procedures or study product occurs, the Sponsor will be monetarily responsible for all costs associated with the follow-up for said event including, but not limited to, medical visits and medication prescribed by a medical professional directly related to the adverse event along with an administration fee that covers the Principal Investigator's time resolving the Adverse Event. If it is determined by Test Facility Management that the Adverse Event is due to negligence on the part of the Test Facility, no cost will be passed through to the Sponsor. The subject under the direction of the Principal Investigator (or designee) may be referred to the nearest acute care facility for treatment. All Adverse Events will be followed to resolution and documented on appropriate Adverse Event paperwork.

14.3.3 Notification

The Sponsor and the reviewing IRB will be notified of all adverse event/experiences that require treatment within 2 business days. Any Serious or Unexpected Adverse Event/Experience that occurs during the study must be reported immediately by the Principal Investigator (or designee) to the Sponsor and the reviewing IRB, followed by written notification within 1 business day of the information being reported to the investigative study team.

Sponsor Notification of Serious Adverse Event:

Primary Contact:	
Telephone:	
Email:	
Secondary Contact:	
Secondary Contact: Telephone:	

The Principal Investigator, [name], and Medical Expert, are required to review all unanticipated problems involving risk to volunteers or others, serious adverse events, and all subject deaths associated with the protocol and provide an unbiased written report of the event. At a minimum, the Principal Investigator and Medical Expert must comment on the outcomes of the event or problem, and in the case of a serious adverse event or death, comment on the relationship to participation in the study.

14.4 **Anticipated Reactions**

The risks associated with this test are primarily related to application of the test materials, and/or the test methodology. Mild abrasion may occur due to cylinder sampling. Folliculitis may be present from clipping. Mild skin irritation is anticipated and in some cases mild to heavy erythema, swelling, itching, cracking, peeling, or in rare cases, blistering and/or an allergic reaction might occur.

15.0 STATISTICAL METHODS

Data processing and statistical analysis for this study will be conducted by the BD statistical group based on the final monitored data provided by the Testing Facility to the BD statistical group.

Details of the statistical analysis will be provided in a separate statistical analysis plan.

Data sets analyzed

The full intent to treat (ITT) data set (all randomized subjects) will be used for the safety analysis.

A modified Intent to Treat (mITT) data set will be used for efficacy analyses. Inclusion for the mITT data set is evaluated for each body area (left and right for the groin and abdomen). For each body area, if the treatment day baseline bacterial count requirements are in the range of 3.11 to 5.50 log₁₀/cm², inclusive, on the abdomen and 5.50 to 7.50 log₁₀/cm², inclusive, on the groin, then the data from that body area are included in the mITT data set. Efficacy analyses will also be conducted on the Per Protocol data set as supportive analyses when Per Protocol data are different from mITT data.

- For responder rate, missing data will be treated as non-responders in the mITT data, while in the Per Protocol data, missing data will not be imputed and will be excluded from the responder rate Per Protocol analysis.
- For log reduction, missing data will not be imputed for either mITT data or Per Protocol data and will be excluded from log reduction analysis.

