7.1 Primary Analysis

A modified intent to treat (mITT) data set will be used for efficacy analyses. Inclusion for the mITT data set is evaluated for each body area (left and right for the groin and abdomen). For each body area, if the treatment day baseline bacterial count requirements are in the range of 3.11 to 5.50 log₁₀/cm², inclusive, on the abdomen and 5.50 to 7.50 log₁₀/cm², inclusive, on the groin, then the data from that body area are included in the mITT data. Efficacy analyses will also be conducted on the Per Protocol data set as supportive analyses when Per Protocol data are different from mITT data.

- For responder rate, missing data will be imputed as non-responders in the mITT data, while in the Per Protocol data, missing data will not be imputed and will be excluded from the responder rate Per Protocol analyses.
- For log reduction, missing data will not be imputed for either mITT data or Per Protocol data and will be excluded from log reduction analyses.

Log₁₀ reductions for the analysis of the efficacy will be calculated by subtracting the post-test material application log₁₀ recovery from the Treatment Day baseline log₁₀ recovery. Log₁₀ reductions will be calculated for all study materials for both the groin and the abdomen at both the 10 minute and 6 hour sample times.

The primary measure of antimicrobial efficacy is the responder rate. Responder status is calculated separately for each treatment, body area (abdomen and groin), and each post-application sample time. At the 10-minute sample time a subject is defined as a responder for the groin if they show at least a $3 \log_{10}$ reduction from baseline skin flora counts; a subject is defined as a responder for the abdomen if they show at least a $2 \log_{10}$ reduction from baseline skin flora counts. At the 6-hour sample time a subject is defined as a responder if they have a microbial mean \log_{10} reduction from baseline that is greater than 0. The primary efficacy target is to show a 70% responder rate for each body area and post-application sample time for the Investigational Product.

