7.2 Secondary Analysis

Based on the mITT data / Per Protocol data, at the 10-minute sample time, the efficacy targets for the Investigational Product are mean \log_{10} reductions from baseline skin flora counts ≥ 3 for the groin and ≥ 2 for the abdomen. At the 6-hour sample time, the efficacy targets are mean \log_{10} reductions from baseline that are greater than 0 for both groin and abdomen.

Log₁₀ reductions and responder rates will be compared between study materials. The Investigational Product and Active Control should demonstrate greater mean log₁₀ reductions from baseline at both 10 minutes and 6 hours and greater response rates at 10 minutes relative to the Vehicle Control.

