7.4 Sample Size Justification

A sufficient number of volunteers will be enrolled in the screening phase such that the total numbers of evaluable samples collected from groin and abdominal regions are not less than 48 evaluable test sites from Investigational Product and Active Control and 16 evaluable test sites from the Vehicle Control arm arms (minimum of 112 each for groin and abdominal regions). Subjects must satisfy all Screening Day and Treatment Day Inclusion/Exclusion Criteria prior to screening sample collection and Treatment Day procedures. If the required numbers of subjects do not qualify from the initial screening group, additional volunteers will be recruited.

This is a Phase 2 study to assess the immediate and persistent antimicrobial effect of the Investigational Product relative to the log₁₀ reduction and response rate standards set forth in the Food and Drug Administration Tentative Final Monograph (TFM) for *Effectiveness Testing of a Patient Preoperative Skin Preparation* (FR 59:116, 17 June 94, pp. 31450-31452) and inform design of future Phase 3 pivotal efficacy studies. Therefore, no sample size calculation was performed to provide statistically-powered evidence of efficacy as part of this study. The sample size is deemed adequate for these purposes.

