15.2 Secondary Analysis

The following descriptive statistics for \log_{10} CFU/cm² reductions will be computed for each product tested, grouped by anatomical site and each post application sampling time point (10 minutes and 6 hours): mean, median, standard deviation, minimum, maximum, and count.

The mean \log_{10} reductions of the Investigational Product, Active Control, and Vehicle Control will be compared to the FDA TFM standards at 10 minutes and 6 hours. The efficacy targets for the Investigational Product are mean \log_{10} reductions from baseline skin flora counts ≥ 3 for the groin and ≥ 2 for the abdomen. At the 6-hour sample time, the efficacy targets are mean \log_{10} reductions from baseline that are greater than 0 for both groin and abdomen.

Antimicrobial activity will be compared using log₁₀ reductions and responder rates between the Investigational Product, Active Control and Vehicle Control for each body area at both post treatment sampling times. Differences in log₁₀ CFU/cm² reductions between treatments and confidence intervals for will be produced by a mixed model ANOVA. Two-proportion test will be used to test differences in responder rates between treatment groups. The goal is that both the Investigational Product and Active Control demonstrate greater mean log₁₀ reductions from baseline at both 10 minutes and 6 hours and greater response rates at 10 minutes relative to the Vehicle Control.

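### Counting missing responder results as failures is cautious against the 70% standard, but in the between-product comparisons it can favour the tested product when comparator results are disproportionately missing

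*Combined protocol and SAP*

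**What the plan says.** - **Missing-data rule.** Section 15.0 states "For responder rate, missing data will be treated as non-responders in the mITT data", and Section 7.1 has the same rule. Neither distinguishes between arms or between uses of the data.
- **First use.** Section 7.1: "The primary efficacy target is to show a 70% responder rate for each body area and post-application sample time for the Investigational Product". Section 15.1 compares all three products with 70%.
- **Second use.** Section 7.2 says that "responder rates will be compared between study materials", and Section 15.2 adds: "Two-proportion test will be used to test differences in responder rates between treatment groups". This is done for each body area at both post-treatment times. The response-rate goal is narrower: "greater response rates at 10 minutes relative to the Vehicle Control".
- **Supportive analysis.** Section 15.0: "Efficacy analyses will also be conducted on the Per Protocol data set as supportive analyses when Per Protocol data are different from mITT data". In that set, "in the Per Protocol data, missing data will not be imputed and will be excluded from the responder rate Per Protocol analysis".
- **Size.** Section 7.4 requires "not less than 48 evaluable test sites from Investigational Product and Active Control and 16 evaluable test sites from the Vehicle Control arm", for groin and abdomen each.
- **What makes a result missing.** Samples are plated in duplicate (13.7, 13.8). If one plate is uncountable, the other plate's count is used (13.10).

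**The concern.** One imputation rule serves two questions that need caution in opposite places. Against a fixed 70%, scoring a missing product result as failure can only lower the product's rate. In a difference between two products, scoring a missing comparator result as failure lowers the comparator and enlarges the difference. That is anti-conservative for the claim being tested.

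The Vehicle arm is where this matters most, because it has a third as many sites as each active arm. The study is meant to inform Phase 3 design, so a Vehicle contrast that depends on one absent result could mislead that planning. Active Control results that are missing when the Investigational Product is compared with it act in the same direction, but each carries less weight.

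**Working it through.** **Inputs.** Site and subject numbers come from Sections 7.4 and 13.3. The plan gives no alpha, sidedness, test variant or expected response rates for the efficacy comparisons. I assume two-sided 0.05 and the pooled two-proportion z-test, then check other variants. All response counts and rates below are assumptions. Sites are treated as independent, as the planned test does.

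**1. The plan's own figure.** 40 subjects receive A and B, 8 receive A and C, and 8 receive B and C. Sites: A = 40 + 8 = 48; B = 40 + 8 = 48; C = 8 + 8 = 16. Total 112 = 56 × 2, as stated.

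**2. Weight of one site.** Vehicle: 1/16 = 6.25 points. Investigational Product or Active Control: 1/48 = 2.1 points.

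**3. The 70% standard.** Take 33 product responders and one missing product result. Excluded: 33/47 = 70.2%, target met. Imputed: 33/48 = 68.75%, target missed. The rule is conservative here.

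**4. Vehicle comparison.** z = (p1 − p2) / √[p(1 − p)(1/n1 + 1/n2)], with p the pooled proportion. The product has 44/48 = 91.7%, and one of 12 Vehicle responders goes missing.

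| Handling | Vehicle | Difference | Pooled p | SE | z | p-value | Fisher p |
|---|---|---|---|---|---|---|---|
| Complete data | 12/16 | 16.7 points | 56/64 = 0.875 | 0.0955 | 1.75 | 0.081 | 0.099 |
| Missing = failure | 11/16 | 22.9 points | 55/64 = 0.859 | 0.1004 | 2.28 | 0.022 | 0.036 |
| Missing excluded | 11/15 | 18.3 points | 55/63 = 0.873 | 0.0985 | 1.86 | 0.063 | 0.084 |

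**5. Dependence on the test.** With a continuity correction this example does not flip (0.190, then 0.062). I therefore enumerated every table with at least 34/48 product responders and one missing Vehicle result, looking for p ≥ 0.05 when it is excluded and p < 0.05 when it is imputed. Such tables number 11 (pooled z), 10 (continuity-corrected), 10 (unpooled z) and 8 (Fisher). Flips occur under every variant, though not in the same tables. The lowest Vehicle count among them is 6/15 = 40%.

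**6. How often.** Chance that one missing Vehicle result flips the pooled z-test, by assumed true rates (product v Vehicle):

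- 85% v 55%: 12%
- 90% v 70%: 17%
- 95% v 80%: 15%
- 85% v 20%: 0.06%

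**7. False positives in the product's favour.** Equal true rates, one Vehicle result missing, pooled z, nominal 0.025:

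| True rate | Excluded | Imputed as failure |
|---|---|---|
| 70% | 0.031 | 0.052 |
| 80% | 0.031 | 0.073 |
| 90% | 0.039 | 0.088 |

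**8. Direction.** Let m1 and m2 be the missing fractions for product and Vehicle. The imputed difference is p1(1 − m1) − p2(1 − m2) = (p1 − p2) − (p1·m1 − p2·m2). It exceeds the true difference only when p2·m2 > p1·m1. With 85% v 55% and 5% missing in both arms, the expected z is 2.24 imputed against 2.43 excluded, so equal missingness works against the product. A missing product result does too: 40/48 v 9/16 has Fisher p = 0.041, and 39/48 v 9/16 has 0.092.

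**The case against.** The strongest reply is that the problem is conditional, secondary and partly covered already.

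- **A reader might infer that one lost Vehicle plate is enough.** It is not. The surviving duplicate is used, so a whole sample or both plates must be lost.
- **A reader might infer that the rule generally helps the product.** It does so only when comparator responders are lost disproportionately, and the documents give no reason to expect that. However, equal counts are not equal fractions. If one responder is lost from each arm in the example, 43/48 v 11/16 gives pooled z p = 0.047 (Fisher 0.104).
- **A reader might infer that the response-rate goal against Vehicle is exposed at both times.** That goal is set for 10 minutes only, where a Vehicle response needs a 2-log (abdomen) or 3-log (groin) reduction. If few Vehicle sites achieve that, a flip is very unlikely. At 6 hours the goal against Vehicle concerns mean log reduction, where missing values are not imputed.
- **The Per Protocol run excludes missing results.** In the example it would show p = 0.063 if nothing else differed, so it may well expose a flip. It is supportive only, nothing says what follows if the two analyses disagree, and exclusion never tests a missing Vehicle result as a response. It would go too far to say that it also drops sites for other reasons, because the supplied text does not define the Per Protocol set.
- **The study is an unpowered Phase 2 trial, and no decision is tied to a p-value against Vehicle.** This stands, and it argues against a strict rule that every analysis must agree before a difference is reported.
- **Section 15.0 defers details to a separate statistical analysis plan.** A sensitivity run might be there; the supplied text contains none.

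**Conclusion.** The point holds in a limited form. The rule suits the 70% standard but can be anti-conservative in the Section 15.2 responder comparisons when comparator results are missing disproportionately. One missing Vehicle result moves the Vehicle rate by up to 6.25 points and can carry the comparison across 0.05. With equal true rates of 70% to 90%, it raises the pooled-z false-positive rate in the product's favour to between 0.052 and 0.088, against 0.031 to 0.039 if the result is excluded.

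This rests on an assumed two-sided 0.05, assumed response rates, independent sites and at least one missing Vehicle result. The exposure lies mainly at 6 hours, where any reduction counts as response and the Vehicle rate may be high. It is small at 10 minutes if Vehicle response is low. With no missing comparator results, the comparator rates are unaffected. The primary analysis is not in question, and this is an optional improvement.

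**What to change.** Keep the missing-as-failure rule for the 70% standard. For the Section 15.2 responder comparisons, prespecify one sensitivity run of the same two-proportion test. In it, a missing comparator result (Vehicle, or Active Control when the Investigational Product is compared with it) counts as a response, and a missing result for the tested product stays a non-response. Report it beside the mITT result and the result with missing values excluded. Describe any difference that does not hold across the three as dependent on missing data. In the example, the added run returns 44/48 v 12/16, p = 0.081, beside 0.022 and 0.063.

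The cost is a short addition to the statistical analysis plan and one extra run. Some comparisons will look slightly less favourable to the tested product. Where Vehicle response is rare, counting a missing Vehicle result as a response is a pessimistic bound and should be labelled as one.
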